6.1 Dose Regimen and Dose Groups: Intervention groups

6.1.1 Placebo Group: All participants in the placebo arm will receive the multivitamin supplement and the cognitive battery tests and structural and resting-state functional imaging at baseline and 3 months. The placebo group used herein will allow us to generate information regarding the reliable change index, so information regarding the naturalistic change in cognitive performance, as well as the potential for practice effects to influence mean-level change data, across the follow-up period is important.

6.1.2 Nutritional Supplement Group (NS): The choice of the supplement to use in this trial is based on relevant research supporting the various components as well as the use of a commercially available standardized dietary supplement of anthocyanins and n-3 fatty acids. The supplement to be used is a standardized formulation of blueberry extract VitaBlue® (40% polyphenolics, 12.5% anthocyanins from blueberries. The supplement will in addition include Lovaza® (omega-3-acid ethyl esters), an FDA-approved prescription omega-3 provides prescription-only potency and purity with each 1-gram Lovaza® (omega-3-acid ethyl esters) gel capsule contains 90% omega-3-acid ethyl esters; 84% eicosapentaenoic acid (EPA) and docosahexaenoic acid (DHA) ethyl esters. Lovaza® is provided by GlaxoSmithKline, who has authorized the FDA center for Drug Evaluation and Research, Division of Metabolic and Endocrine Drug Products to reference Lovaza® Capsules IND # 45,998. An investigator-initiated IND has been obtained by PI for use of these agents in this clinical trial (IND # 116424). Subjects in the supplements treatment arm of the study will be given in the same fashion and time table to the "placebo" patients as the active treatment patients.

6.2 Agent Administration: Intervention will be administered to the patient on an outpatient basis and self-administered by the participants. The daily dose of will be taken in divided doses (Lovaza® 2 tablet BID and Vitablue™ 2 tablet TID). On the day of monthly follow-up visit, capsules should be taken within 4 hours of visit and blood draw for required lab work.

Two bottles containing Lovaza and 1 bottle of anthocyanins capsules will be dispensed to all participants upon randomization with adequate number of capsules, to ensure that the subject has sufficient study drug to last until the next planned clinic visit. At baseline and at each monthly visit up to the 3-month final visit, participants will receive these supplements in person to take home with them. At that point, participants will receive instructions regarding how many supplement pills they are to take a day.

Schedule of dose administration of study agents

Arm of Study	Breakfast	Lunch	Dinner
Treatment arm	2 tablets Lovaza 2 tablets Vitablue	2 tablets Vitablue	2 tablets Lovaza 2 tablets Vitablue 1 tablet multivitamin/mineral
Placebo arm	4 tablets matching placebo tablets	2 tablets matching placebo	4 tablets matching placebo tablets 1 tablet multivitamin/mineral

6.3 Contraindications: COGNUTRIN ingredients - n-3 fatty acids may be contraindicated in subjects with bleeding disorders and anthocyanins may be contraindicated in people who are sensitive or allergic to berries.

During study participation, subjects will be instructed to limit their consumption of the following berries to 1 cup per day: blackberry, blueberry, chokeberry, black currant, elderberry, and black raspberry. They will be asked to limit their consumption of the following omega 3's to 2-3 servings (4 oz per serving) a week: walnuts, flaxseed oil, canola oil, fish oils, and fatty fish such as salmon, trout, mackerel, herring, sardines, pilchards, kipper, eel, whitebait, fresh tuna, anchovies, swordfish, bloater, cacha, carp, hilsa, jack fish, katla, orange roughy, and pangas.

6.4 Concomitant Medications: During study participation, subjects will be instructed to suspend consumption of additional supplements containing anthocyanins or omega 3's. Subjects are considered enrolled in the trial from the time that the informed consent document is signed until the time that the subject is off study. All medications (prescription and over-the-counter), taken by the participant while on study will be documented on the concomitant medication CRF and will include: start and stop date, dose and route of administration, and indication.

6.5 Dose and Toxicity Management: We will ensure that our protocol and informed consent comply with FDA recommendations. In addition, we have planned monthly visits to monitor daily symptoms monitor and will perform an interview for adverse events, unusual symptoms, change in medical condition and concomitant medications use. Any abnormality observed will be communicated by the research coordinator to the study MD for evaluation and for continuation in the study. Subjects in the study will be dropped from study until which time the symptom is determined to be unrelated to the study agent as determined by the study MD. We will provide each subject with a 24- hour contact phone number and specific instruction on contacting the research team including the MD in this study. In addition, evaluation of safety in this subject population has been added as a specific aim of the trial with a formal comparison of safety between active and placebo arms, further illustrating our commitment to ensuring subject safety in this and future clinical trials.

A patient's treatment will be discontinued in any of the following circumstances: (a) Allergic reaction to product; (b) Dramatic change in stool frequency; (c) Start of other treatments that may cause malabsorption; (d) Request of patient of MD or patient; (e) Unusual symptoms reported during follow-up or other unusual symptoms or blood work results observed during the study period; and, (f) Persistent nausea not controlled with antiemetics. There are no reductions in the Cognutrin® dose. If adverse events occur that require holding Cognutrin ® (until etiology is determined), the dose will remain the same once treatment resumes. Any toxicities associated or possibly associated with Cognutrin ® treatment will be managed according to standard medical practice. Subjects will be assessed clinically for toxicity prior to, during intervention on a monthly basis and at end of intervention. If >grade III toxicity occurs because of Cognutrin ® at any time during the study, treatment with Cognutrin ® will be discontinued. We will also inquire about hypersensitivity to fish/and or shellfish and symptoms of atrial fibrillation at each visit. All subjects will be followed by their medical oncologists for their cancer treatment, using the routine surveillance guidelines as established by the Cancer Center during the study.

There are no alternative agents that are currently available to treat or ameliorate cognitive impairment observed in this target population. To date, interventions with cognitive training alone, pharmacological agents to treat chemotherapy-induced anemia, psycho stimulants and antioxidant therapies with Vitamins A, C and E have not demonstrated efficacy nor safety in treating CI. We and others have demonstrated in preclinical and clinical trials that plant-based substances and n-3 fatty acids with potent antioxidant and anti-inflammatory properties can be detected in plasma and serum, cross the blood-brain barrier, localize in various brain regions important for learning and memory such as cerebellum, striatum

and hippocampus and increase neurogenesis. However, these interventions have not been evaluated to ameliorate CI in cancer patients treated with chemotherapy. The results of this study may inform the design of a well-powered clinical trial to test the effectiveness of this intervention to ameliorate these late effects of cancer treatment and ultimately improve quality of survival in this patient population. However, no guarantee of personal benefit based on participation will be made to subjects recruited in this study. Instead, participants will be told that results are expected to contribute to increased knowledge about possible interventions to remediate chemotherapy-induced changes in cognitive performance. Among persons in the nutritional supplementation intervention conditions, based on existing evidence from the ageing literature, some improvements to cognitive performance are anticipated.

On the other hand, the risks to participants of this study can be divided into three groups a) risk due to collection of blood, b) potential risk due to study agent intake; c) Magnetic resonance Imaging (MRI). We have taken careful steps to implement **procedures for minimizing and protecting against potential risks:**

(a) Reduce risks of specimen collection: Participants undergoing venipuncture typically experience brief pain during needle insertion; occasionally experience bruising or the need for additional needle sticks to access “good vein”, and rarely experience an infection at the site of needle insertion. Sterile equipment, accepted clinical practices, and trained; experienced staff will be used to reduce the risks of specimen collection. In addition the site will be cleaned before drawing blood, pressure will be applied until the bleeding stops and a sterile dressing will be used to cover the puncture site.

(b) Reduce risk due to study agent: Based upon our team’s considerable experience administering anthocyanins and n-3 fatty acid supplementation in preclinical and clinical trials, we have proposed periodic monitoring of organ function (CBC, CMP) including liver function tests throughout the study. Moreover, all of the substances in the nutritional supplements are found in everyday foods and are not at levels that greatly exceed a typical dietary intake. We have obtained detailed information and potential side effects of each of the agents used in the study and paid attention to the criteria for inclusion and exclusion and dose to reduce side effects as follows: **Study Agent Lovaza®** There is no established Dietary Reference Intake for n-3 fatty acids, yet the Adequate Intake (AI) is set at 1.6 and 1.1 grams/day for men and women respectively. While intake in the United States occurs at much lower than the proposed AI and no signs of deficiency are observed, the AI is proposed to provide optimal health benefits associated with consuming n-3 fatty acids. There is no Upper Limit established for n-3 fatty acids. In early studies using fish oil capsules, we and others have demonstrated the safety of administering 2-6 gms of EPA per day. Anticachectic effects were seen with these doses, with no adverse effects, however, there was no greater response with 6 gms per day relative to 2-4 grams/day. Therefore, the dose selected for this pilot clinical trial, 4 grams per day is comparable to the safe but effective dosage used in our preliminary studies and that of others. Currently prescription doses of 4 grams a day of Lovaza® is used and approved by the FDA to treat hypertriglyceridemia. Furthermore, one, 3 to 4 oz serving of cold water fish such as salmon or sardines contains approximately 1.0-1.5 gms of n-3 fatty acids. The participant will be provided packages of the agent in a capsule form and instructed on compliance, intake, duration of intervention, and monitors to be completed by the research staff. Subjects will be instructed to consume 4 gm Lovaza® in a divided dose (2 gm in the morning, 2 gm at night, to provide a total of 4 gm/day) with meals for a period of 3 months. **Blueberry anthocyanins (VitaBlue):** Similarly, there is no established Dietary Reference Intake of the constituents of anthocyanins. The average daily consumption of anthocyanins in a western diet is estimated to be 100 mgs/day. Anthocyanins are rapidly absorbed and metabolized extensively following a moderate-to-high oral dose in humans. Studies have indicated anywhere from 4-6 hours half-life with complete excretion of parent compound as well as metabolites within 24 hours both in urine and plasma, indicating the need for a dose every 6- 8 hours to have consistent exposure¹²¹. Similarly administration of anthocyanins at doses ranging from 0.5-2.0 grams daily for 7 days in colorectal cancer patients with dose dependant concentrations detected in plasma and urine with no toxicities. Studies utilizing anthocyanins at doses of 1.4 grams/day (Mitroslect, Indena S.p.A.) administered as 0.47 grams/capsule TID are currently in progress to provide active cellular antioxidant protection, inhibit inflammatory gene expression and consequently protect against oxidant-induced and inflammatory cell damage and cytotoxicity in obesity-induced inflammation and insulin resistance in 40-60 year old males for 21 days. In summary, repeated administration of anthocyanins exerts pharmacodynamic effects and generates concentrations of anthocyanins in human plasma as well as urine with no toxicity. We will thus use a dose of 0.47 grams/capsule dose of anthocyanins TID to total 1.4 grams per day, similar to the dose used in these chemoprevention trials.

Nevertheless, we will record adverse events and will develop a data safety and monitoring plan to ensure that study participants are not negatively affected by study compounds. We will in addition obtain symptoms and concomitant medications that may be potentially related to study agent intake using daily monitors. All of the substances in the nutritional supplements are found in everyday foods and are not at levels that greatly exceed a typical dietary intake. Nevertheless, we will observe and report adverse events and will develop a data safety and monitoring plan to ensure that study participants are not negatively affected by study compounds. Our group is currently involved in several active clinical trials where these agents are being used and under IND approval from the FDA. We will keep abreast of the literature in the area of potential drug-drug, drug-nutrient interactions and other contraindications in the evolving research and will amend the study appropriately to ensure subject safety.

(c) Risks due to MRI: For most people, there is no danger associated with having an MRI scan. However, there may be some risk of psychological distress for the individuals posed by the confining environment of the scanner. We will therefore verify that participants are not claustrophobic, thereby reducing the probability of claustrophobia. The scanning environment poses potential risk from the magnet; specifically that metallic objects brought into the scanning room are dangerous to the individual. However the well-established Moffitt Cancer Center and University Diagnostic Institute protocol for treatment of patients in this environment minimizes risk.

Other: The research team has considerable experience with administering cognitive tests to young and older adults and in all cases, participants will be encouraged to do “their best”, which seems to minimize test taking anxiety. Experienced personnel will administer all self-report and cognitive performance measures. The research study staff will carefully monitor participants' reactions and provide information upon request. All participants will be provided with [name] name and telephone number.

Based on the unavailability of effective and safe treatments to ameliorate cognitive impairment resulting from chemotherapy and the potential benefit a study such as this can provide, combined with the careful attention paid to minimize and eliminate risks due to participation, the benefits outweigh the risks.

Adverse events requiring delays or permanent discontinuation of Cognutrin® are listed in the table below:

Event	Action
Grade 1 & 2 constitutional, dermatological, gastrointestinal (GI), metabolic and pain symptoms Examples: Rash Allergic rhinitis, cough, bronchitis. Abdominal Pain Belching/Gas Nausea/Vomiting Diarrhea	No Action Required Inform MD Document event in research and medical record
Grade 3	Discontinue Cognutrin ®/Notify Study PI
Grade 4	Discontinue Cognutrin ®/Notify Study PI
Grade 2, 3, or 4 abnormal liver function tests ^{1,2} as determined by NCI CTC version 4.0	Discontinue Cognutrin ®/Notify Study PI and Monitor until it returns to normal

1. Tests used to monitor liver function include: albumin, total and direct bilirubin, alkaline phosphatase, AST, ALT, total protein, PT/PTT.)
2. In the event that PT/PTT is abnormal due to anticoagulant therapy, treatment and/or drug discontinuation will be at the discretion of the site investigator/MD.

Regardless of the reason for holding study drug treatment, the maximum allowable length of treatment interruption is 1 week. Interruption of intake of >1 week will result in discontinuance of subject from the study. Patients who have an ongoing Cognutrin ®-related Grade 3-4 or serious adverse event at the time of discontinuation from study treatment will continue to be followed until resolution of the event or until the event is considered irreversible by the study MDs.

In addition, a standard multivitamin/ mineral preparation will be provided free of charge during the study duration, to assure a consistent baseline intake of essential vitamins and minerals among all study participants during the study period and to encourage subjects from not using other supplements that may contain components of the study agents. Subjects in the treatment and placebo arms will be provided these multivitamin/mineral supplements and instructed to consume 1 tablet daily with the dinner meal.

In our experience with cancer survivors both clinically and in research studies, over 75-85% of breast cancer survivors use a multivitamin/mineral supplement. Several of these supplements have added ingredients including botanicals and biologics from unknown as well as known sources. The quality, content, standardization techniques, safety as well as stability of the content of these supplements have been a challenge to our team. In order to provide a standard dose to all subjects in the study .ensure safety and prevent any overdosing on other supplements, similar to the content of COGNUTRIN, we have provided a standard multivitamin/mineral to the subjects in our clinical trials with botanicals and biologics.

Our group is currently involved in several active clinical trials where these agents are being used and under IND approval from the FDA. We will keep abreast of the literature in the area of potential drug-drug, drug-nutrient interactions and other contraindications in the evolving research and will amend the study appropriately to ensure subject safety.

The research team has considerable experience with administering cognitive tests to young and older adults and in all cases, participants will be encouraged to do “their best”, which seems to minimize test taking anxiety. Experienced personnel will administer all self-report and cognitive performance measures. The research study staff will carefully monitor participants' reactions and provide information upon request. All participants will be provided with [name] name and telephone number to clarify or answer any questions.

6.6 Adherence/Compliance: During study participation, subjects will be asked to: self-administer the study medication; complete diet recall forms at specified time periods (baseline, 1, 2 and 3 months); avoid consumption of additional nutritional supplements and multivitamins containing the recommended daily allowance (RDA) of Vitamin D. Subjects are expected to: maintain $\geq 85\%$ compliance with study agent intake; comply with dietary, medication and supplement restrictions; and complete the diet recall forms to the best of their ability. Subjects will be interviewed at the monthly scheduled time points, at which time pill counts will be performed to verify compliance with study requirements. Subjects discovered not to be complying with study requirements will have the requirements re-explained to them.

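### Section 6.5 requires stopping treatment for an allergic reaction to the product at any grade, but its action table asks for no action on grade 1-2 rash or allergic rhinitis and makes no exception for reactions attributed to the product

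*Combined protocol and SAP*

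**What the plan says.** Two parts of Section 6.5 (Dose and Toxicity Management) bear on mild allergic reactions.

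The narrative lists circumstances (a) to (f), any one of which ends treatment. The first reads "treatment will be discontinued in any of the following circumstances: (a) Allergic reaction to product". The trigger is a causal judgement, the wording is mandatory, and no severity grade is attached.

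The action table is introduced with "Adverse events requiring delays or permanent discontinuation of Cognutrin® are listed in the table below". Its first row covers "Grade 1 & 2 constitutional, dermatological, gastrointestinal (GI), metabolic and pain symptoms Examples: Rash Allergic rhinitis, cough, bronchitis", followed by gastrointestinal examples. The action for that row is "No Action Required Inform MD Document event in research and medical record". Discontinuation in the table begins at grade 3, or at grade 2 for abnormal liver function tests. Of the two footnotes, one lists the liver tests and the other deals with PT/PTT in patients on anticoagulants.

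**The concern.** The table is what staff are likely to consult when a patient reports a symptom, and its lead-in presents it as the list of events that call for a delay or a stop. A coordinator or nurse who finds rash or allergic rhinitis in the grade 1-2 row could reasonably conclude that dosing goes on. For a reaction attributed to the product, the narrative requires the opposite.

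Allergy is a risk that the protocol itself names. Section 5.1.1 says that blueberries can cause food-allergy symptoms in sensitized people. It describes one woman who reacted to lingonberry, a related fruit: the first symptoms passed, and those on re-exposure to a very small amount were more severe. Section 6.3 notes a possible contraindication in people sensitive to berries. The blueberry capsules are self-administered three times a day (Section 6.2), so continuing means repeated exposure. Under Section 7.7.8, the nurse who drew blood reviews adverse events with the patient at Months 1 and 2 and the principal investigator signs the log. The medical oncologist's scheduled review of events during treatment comes at Month 3. At stake are a patient's safety after a mild reaction and consistent handling of such patients.

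**Working it through.** No arithmetic applies, and the plan states no figure to reproduce. The check sets the two rules side by side.

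| | Narrative, criterion (a) | Table, grade 1-2 row |
|---|---|---|
| Trigger | Allergic reaction attributed to the product | Symptom type and grade; rash and allergic rhinitis named |
| Grade limit | None | Grades 1 and 2 |
| Attribution | Required | Not mentioned |
| Action | Discontinue (mandatory) | None beyond informing the physician and documenting |

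Applying both rules to the possible cases:

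1. *Grade 3 or 4 reaction to product.* Criterion (a) stops treatment, and so do the grade 3 and grade 4 rows. The rules agree.
2. *Grade 1-2 rash or rhinitis not judged a reaction to product.* Criterion (a) is not met, and the table asks for no action. The rules agree.
3. *Grade 1-2 rash or rhinitis judged an allergic reaction to product.* Criterion (a) stops treatment, while the table requires no action beyond notification and documentation. The rules conflict.

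The conflict is confined to case 3. I then looked for text that would resolve it:

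- **Row and footnotes.** Neither mentions allergy or attribution.
- **Order of precedence.** Section 6.5 states none between narrative and table.
- **Physician review.** The narrative sends any abnormality to the study physician, and criterion (d), "d) Request of patient of MD or patient", lets the physician end treatment. This permits a stop without requiring one.
- **Off-agent and off-study grounds.** Section 8.3 lists investigator discretion and medical contraindication, and Section 8.4 lists an adverse event. Section 8.3 says that participants may stop, and neither section tells staff using the table that a mild product allergy must end treatment.
- **Eligibility.** Section 4.2 excludes known allergy to the components. That lowers the chance of an event but does not say what to do when one occurs.

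None of these restores the mandatory stop for someone working from the table.

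**The case against.** The strongest reply is that the two texts do different jobs. The row sorts symptoms by grade before anyone has judged the cause, while criterion (a) is a causal rule that is sufficient by itself. The row does not tell staff to continue dosing, and it does require that a physician be informed. Once that physician judges the event a reaction to product, criterion (a) applies. Section 6.5 also has toxicities possibly related to treatment managed by standard medical practice and gives patients a 24-hour contact number. On this view, harm needs someone to follow the table and overlook the narrative.

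Most of this stands. It is probably what the authors intended, and it is why the risk is small. It does not remove the conflict, because the table presents itself as the list of events that need a delay or stop, and the safeguards allow what criterion (a) demands.

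A reader might infer more than the documents support:

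- **That mild rash or rhinitis is mishandled in general.** Only events judged to be an allergic reaction to product get conflicting instructions.
- **That every mild symptom should trigger removal.** Section 6.5 does say "Subjects in the study will be dropped from study until which time the symptom is determined to be unrelated to the study agent", with no grade limit. But it also says "If adverse events occur that require holding Cognutrin ® (until etiology is determined), the dose will remain the same once treatment resumes", which implies that only some events need a hold. The first sentence is loosely drafted and is not a rule for all mild symptoms.
- **That the nausea criterion is a second conflict of the same weight.** Criterion (f), "f) Persistent nausea not controlled with antiemetics", is much narrower than the row's general nausea example. A specific stop rule beside a general symptom row is ordinary drafting.
- **That serious reactions are likely.** The re-exposure evidence is one case with another berry, and Section 5.1.1 expects no adverse effects from this agent.

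**Conclusion.** The concern holds as a minor inconsistency in the safety instructions. For a grade 1-2 rash or allergic rhinitis judged to be an allergic reaction to study product, the Section 6.5 narrative requires discontinuation and the table requires no action beyond notification and documentation, with no exception and no order of precedence.

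Its size cannot be expressed as a number of patients: the documents give neither event rates nor the share of events that would be judged allergic to product. The judgement that the risk is small assumes that criterion (a) is meant to prevail and that the informed physician acts on it.

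The safety endpoint, incidence and severity of adverse events (Sections 8.1 and 12.6), is not affected. Events are recorded whether or not they are related to the agent, and the row itself calls for documentation.

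**What to change.** Add an exception to the grade 1-2 row of the Section 6.5 table: *except events that the study MD judges to be an allergic reaction to study product (active or placebo), or that meet another Section 6.5 discontinuation criterion: discontinue.* Naming both active and placebo product means the rule can be applied without knowing the assignment.

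The exception should rest on the physician's judgement and should not impose a hold for every suspected reaction. Section 6.5 removes a subject from the study after an interruption of more than 1 week, so a compulsory hold could lose women whose reaction is never confirmed. With 20 per arm, each such loss is 1/20 = 5% of an arm.

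The cost is one text amendment, with no new visits, tests or analyses. The downside is possibly a few more early discontinuations for mild reactions, which criterion (a) already requires.
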